### **Hematology and clinical chemistry laboratory parameters**

The following summaries will be produced for hematology and clinical chemistry laboratory data (by laboratory parameter):

- Worst post-baseline CTC grade (regardless of the baseline status). Each subject will be counted only for the worst grade observed post-baseline.
- Shift tables using CTC grades to compare baseline to the worst on-treatment value

- For laboratory tests where CTC grades are not defined, shift tables using the low/normal/high/(low and high) classification to compare baseline to the worst on-treatment value.
- Trends of lab parameter values over time (baseline and selected on-treatment timepoints) should be displayed via boxplots based on time windows and corresponding tables displaying the statistics used for the box plots by the selected time points and the selected lab parameters.

The following listings will be produced for the laboratory data:

- Listings of all laboratory data by subject and visit/time, with CTC grades and classification relative to the laboratory normal range. Lab data collected during the post-treatment period will be flagged.
- Listing of all CTC grade 3 or 4 laboratory toxicities by subject and visit/time

In addition, regardless of the transfusion or G-CSF, laboratory tests (Platelet counts, Hemoglobin, Neutrophil count) value and change from baseline will be listed and summarized in scheduled visits using descriptive statistics (mean, SD, median, interquartile range, and range).

### **Coagulation**

Coagulation assays data (Prothrombin time, international normal ratio, Activated partial thromboplastin time) will be listed.

### **Liver function parameters**

Liver function parameters of interest are Total bilirubin (TBIL) and Direct bilirubin (DBIL), ALT, AST and alkaline phosphatase (ALP). The number (%) of patients with worst post-baseline values as per Novartis Liver Toxicity guidelines will be summarized.

For summaries based on multiple parameters, the results must be obtained from samples collected within maximum 30 days of each other.

The following summaries will be produced:

- ALT or AST > 3xULN and (TBIL or DBIL > 2xULN) and (ALP < 2xULN or missing)
- ALT or AST > 3xULN and (TBIL or DBIL > 2xULN)
- ALT or AST > 3xULN and (TBIL or DBIL > 1.5xULN)
- ALT or AST > 20xULN
- ALT or AST > 10xULN
- ALT or AST > 5xULN
- ALT or AST > 3xULN
- ALT > 20xULN
- ALT > 10xULN
- ALT > 5xULN

- ALT > 3xULN
- AST > 20xULN
- AST > 10xULN
- AST > 5xULN
- AST > 3xULN
- DBIL > 2xULN
- DBIL > 1.5xULN
- TBIL > 2xULN
- TBIL > 1.5xULN
- ALP > 1.5xULN

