6.5.1.2 Dose reduction/interruption due to liver function abnormalities and thrombosis/embolism

Eltrombopag dose may be interrupted when clinically indicated at the discretion of the investigator. Serum ALT, AST and bilirubin (total, direct and indirect) should be measured prior to initiation of eltrombopag, every 2 weeks while adjusting the dose and monthly after establishment of a stable dose. Abnormal serum liver function tests (LFTs) should be evaluated with repeat testing preferably within 48-72 hours (see [Table 6-7](#) and [Section 6.5.2.1](#)). If the abnormalities are confirmed, serum liver tests should be monitored weekly until the abnormalities resolve, stabilize, or return to baseline levels. Alternative causes of LFT elevations, such as hepatitis or concomitant medications (e.g., cyclosporine A) must always be investigated.

NOTE: Eltrombopag is known to cause interference in measurement of total bilirubin, which may lead to falsely increased levels of total bilirubin (see [Section 8.4.1](#)). Please take dose modification decision based on direct (conjugated) bilirubin (DBIL) along with ALT and/or AST (see [Table 6-7](#) below).

[Table 6-7](#) summarizes the recommendations for dose interruption or reduction of eltrombopag in the management of liver function abnormalities and thrombosis/embolism events. For participants who fulfill the criteria of eltrombopag discontinuation in [Table 6-7](#), refer to [Section 9.1](#) for the further action to be taken after discontinuation.

Table 6-7 Guidelines for eltrombopag dose modification based on liver function abnormalities and thrombosis/embolism

Criteria	Action
Isolated AST or ALT elevation	
> ULN - 3 x ULN	Maintain dose level.
> 3 - 5 x ULN	Maintain dose level. Repeat liver function test (LFTs) ^a as soon as possible, preferably within 48-72 hours from awareness of the abnormal results. If abnormal lab values are confirmed upon the repeat test, then monitor LFTs ^a weekly, or more frequently if clinically indicated, until resolved to \leq 3.0 x ULN. Discontinue participant from eltrombopag if elevation is combined with any of the following: 
 • Clinical symptoms of liver injury or evidence for hepatic decompensation • Persistence for \geq 4 weeks
> 5 - 10 x ULN	Interrupt dose.

Criteria	Action

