	
Repeat LFTs^a as soon as possible, preferably within 48-72 hours from awareness of the abnormal results. If abnormal lab values are confirmed upon the repeat test, monitor LFTs^a weekly, or more frequently if clinically indicated, until resolved to $\leq 3.0 \times$ ULN, then:
 
If resolved in ≤ 14 days, then resume at same dose level; If toxicity recurs at same dose, then follow the above guideline and resume dose at a lower dose level (decrease by one level^c)
 
If resolved > 14 days and ≤ 28 days, then decrease one dose level^c
 
If not resolved within 28 days, then discontinue participant from study treatment

$> 10 - 20 \times$ ULN	
Interrupt dose.
 
Repeat LFTs^a as soon as possible, preferably within 48-72 hours from awareness of the abnormal results. Monitor LFTs^a weekly, or more frequently if clinically indicated, until resolved to $\leq 3.0 \times$ ULN. If resolved within 28 days, decrease by one dose level.
 
If not resolved to $\leq 3.0 \times$ ULN within 28 days, then discontinue participant from study treatment.

$> 20 \times$ ULN	
Discontinue participant from study treatment.
 
Repeat LFTs^a as soon as possible, preferably within 48-72 hours from awareness of the abnormal results. If abnormal lab values are confirmed upon the repeat test, monitor LFTs^a weekly, or more frequently if clinically indicated until resolved to baseline or stabilization over 4 weeks.

Combined^b elevations of AST or ALT and direct bilirubin (DBIL)	

For participants with normal baseline ALT and AST and DBIL value, [AST or ALT $> 3 \times$ ULN] combined with [DBIL $> 2 \times$ ULN] without evidence of cholestasis
 
OR
 
For participants with elevated baseline ALT or AST or DBIL, [AST or ALT $> 3 \times$ baseline] OR [AST or ALT $> 5 \times$ ULN], whichever is lower, combined with [DBIL $> 2 \times$ baseline AND $> 2 \times$ ULN]
	
Discontinue participant from study treatment
 
Repeat LFTs^a as soon as possible, preferably within 48 hours from awareness of the abnormal results, then weekly or more frequently (if clinically indicated) monitor LFTs^a, or more frequently if clinically indicated, until ALT, AST or DBIL have resolved to baseline or stabilization over 4 weeks.
 
Evaluate the possibility of DILI (Section 6.5.2.1)

Thrombosis/embolism	

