Deep vein thrombosis, pulmonary embolus, transient ischemic attack (TIA) or stroke, myocardial infarction at any time while on eltrombopag	
Discontinue participant from eltrombopag.
 
If the platelet level is $> 50 \times 10^9/L$ at the time of thrombosis, treatment with enoxaparin or another appropriate anticoagulant is recommended as clinically indicated until the platelet count drops $< 20 \times 10^9/L$ or a standard 3 to 6 month course of anticoagulation is completed.

^a Core LFTs consists of ALT, AST, GGT (Gamma-glutamyl transferase), total bilirubin (direct and indirect), and alkaline phosphatase (ALP)
 
^b "Combined" is defined DBIL increase to the defined threshold concurrently with ALT/AST increase to the defined threshold. If the bilirubin increase is below the defined threshold, guidance for isolated AST or ALT elevation should be followed
 
^c Dose level: for participants ≥ 12 years old, one dose level is 25mg; for participants < 12 years old, one dose level is 12.5mg.
	

Definition of discontinuation: study treatment is permanently stopped earlier than the protocol-planned duration

An isolated bilirubin elevation is not typical for drug-induced liver injury. Bilirubin can be elevated either as part of a “Hy’s law” constellation with a preceding elevation of ALT/AST, or as part of a cholestatic reaction with simultaneous elevation of other cholestatic parameters (ALP, GGT). Isolated bilirubin elevation can be seen in conjunction with drugs that inhibit bilirubin conjugation or excretion, but both scenarios do not typically represent liver injury. Alternative causes of bilirubin elevation, including bilirubin interference (see [Section 8.4.1](#)) should be ruled out before basing dose modification decisions on bilirubin values alone

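### Every combined liver row accepts total bilirubin and pairs samples up to 30 days apart, so no table counts participants at the protocol's own threshold of direct bilirubin concurrent with ALT/AST

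*SAP*

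**What the plan says.** SAP 2.8.3, Liver function parameters, plans three rows that combine transaminases with bilirubin:

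- the basic condition, "ALT or AST > 3xULN and (TBIL or DBIL > 2xULN";
- a stricter row, which restricts that condition to participants whose ALP is under twice its upper limit or was not measured;
- a looser row, which lowers the bilirubin cut-off from 2 to 1.5 times its upper limit.

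For rows that use more than one parameter, "the results must be obtained from samples collected within maximum 30 days of each other". DBIL stands by itself only in single-parameter rows, above 2 and above 1.5 times the upper limit of normal (ULN). The final-analysis SAP repeats the rows and the window unchanged.

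Protocol 6.5.1.2 gives a warning: "Eltrombopag is known to cause interference in measurement of total bilirubin, which may lead to falsely increased levels of total bilirubin". It then tells investigators to decide on dose changes from DBIL together with the transaminases. The combined criterion in Table 6-7 has two branches:

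- **Normal baseline:** ALT or AST above 3×ULN with DBIL above 2×ULN and no evidence of cholestasis.
- **Elevated baseline ALT, AST or DBIL:** ALT or AST above the lower of 3× baseline and 5×ULN, with DBIL above both 2× baseline and 2×ULN.

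Footnote b says that a combined elevation "is defined DBIL increase to the defined threshold concurrently with ALT/AST increase to the defined threshold". Section 6.5.2.1 uses the same DBIL thresholds to trigger the drug-induced liver injury (DILI) work-up, but without the cholestasis clause in the normal-baseline branch.

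**The concern.** The protocol and the SAP measure combined liver injury differently, in three respects: which bilirubin counts, how close in time the two elevations must be, and whether the threshold depends on baseline. The protocol gives a reason for the first: the study drug can disturb the TBIL assay. A participant can therefore enter a SAP combined row on a laboratory artefact, or on two peaks weeks apart. Conversely, a participant who met the protocol criterion through the elevated-baseline branch may not appear in any combined row.

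In a single-arm trial of about 36 participants, these rows are where a reader looks for a hepatic safety signal, and one participant more or less is visible. The protocol attaches consequences to its laboratory criterion (discontinuation, work-up and, once confirmed without another cause, SAE reporting). A reader would expect a count at that threshold, and none is planned.

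**Working it through.** The plan states no figure for these rows, so there is none to reproduce. The check compares the two rules and then sizes one misclassified participant.

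**1. Do the rules classify differently?** The profiles are hypothetical, in multiples of ULN, with AST normal and unchanged throughout and no cholestasis.

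| Profile | SAP row (ALT >3 and TBIL or DBIL >2) | Protocol criterion |
|---|---|---|
| (a) Normal baseline; on study ALT 3.5, DBIL 0.8, TBIL 2.3 from interference | 3.5 > 3 and TBIL 2.3 > 2: **met** | DBIL 0.8 is not > 2: **not met** |
| (b) Baseline ALT 0.5, DBIL 1.2; on study ALT 2.0, DBIL 2.8 | ALT 2.0 is not > 3: **not met** | Limit = min(3 × 0.5, 5) = 1.5 and 2.0 > 1.5; DBIL 2.8 > 2 × 1.2 = 2.4 and > 2: **met** |
| (c) Baseline ALT 2.5, DBIL normal; on study ALT 4, DBIL 2.5 | 4 > 3 and DBIL 2.5 > 2: **met** | Limit = min(3 × 2.5, 5) = 5 and 4 is not > 5: **not met** |

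The disagreement runs both ways. Profiles (b) and (c) do not involve TBIL at all; they arise because the elevated-baseline branch has no SAP row. Such participants can be enrolled: exclusion criterion 4 removes only AST or ALT above 3×ULN.

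**2. How wide is the pairing window?** Table 8-1 schedules visits weekly to Week 8 and then every 2 weeks in the core part.

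- An ALT on Day 29 has nine scheduled visits within 30 days: Days 1, 8, 15, 22, 29, 36, 43, 50 and 57. Day 1 counts as baseline under the SAP, so eight of these are post-baseline.
- An ALT on Day 127 has five: Days 99, 113, 127, 141 and 155.

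**3. The cholestasis condition also differs.** Protocol 6.5.2.1 defines cholestasis as ALP above 2×ULN with an R value (ALT over ALP, each in multiples of ULN) below 2. The SAP row requires ALP below 2×ULN or missing. A participant with ALP above 2×ULN and R of 2 or more is not cholestatic under the protocol, but drops out of the SAP's ALP row.

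**4. What do the planned rows still tell the reader?** Both protocol branches require DBIL above 2×ULN, so the single-parameter DBIL >2×ULN row is an upper bound on the protocol count. The combined row without the ALP condition contains every normal-baseline participant who meets the protocol criterion. Neither row identifies the number.

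**5. Scale of one participant, N = 36.** Exact (Clopper-Pearson) intervals; the same calculation returns the SAP Table 3-1 intervals for 14, 16 and 18 of 36.

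- 0/36 = 0% (95% CI 0 to 9.7)
- 1/36 = 2.8% (0.1 to 14.5)
- 2/36 = 5.6% (0.7 to 18.7)

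**The case against.** The strongest reply is that the two rules serve different purposes. The DBIL instruction governs dose decisions and work-up. The SAP rows are a descriptive screen that the SAP attributes to the sponsor's liver toxicity guidelines, and the protocol's own analysis section promises no combined liver table. A broad screen errs towards sensitivity, and for normal-baseline participants it misses none who meet the protocol criterion. That stands as a reason to keep the rows. It does not supply the missing count, and it does not cover the elevated-baseline branch.

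The 30-day window also has a defence. Liver tests are monthly once the dose is stable, and the note under Table 6-7 describes bilirubin rising after a preceding transaminase elevation. A reader might infer that a strict same-date rule should replace the window. The documents do not support that: footnote b requires concurrence, not a shared sample date, and same-date rows alone could lose staggered rises.

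A reader might also infer that affected participants cannot be matched to those who met the protocol's SAE or discontinuation criteria. That goes too far. Protocol 6.5.2.1 requires cases confirmed on repeat testing, with no alternative cause, to be reported as SAEs under a dedicated term. SAP 2.8.1 tabulates SAEs and AEs leading to discontinuation, and SAP 2.8.3 lists all laboratory values by subject and visit. What is absent is a prespecified programmatic count at the laboratory threshold.

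**Conclusion.** The point holds as a gap in the descriptive safety tables. The combined rows can misclassify participants in either direction relative to the protocol's laboratory criterion, and no row reports how many met it. No efficacy estimate, hypothesis test or stopping rule depends on these rows, so this is an inexpensive improvement and not a flaw in the trial's main conclusions.

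Two stronger readings should be resisted.

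- **That the counts are inflated.** The protocol says interference may raise TBIL. Its Section 8.4.1 also considers misleadingly low TBIL, and profile (b) shows a case the SAP row misses. The net direction is not known.
- **That the number of false cases can be sized.** One could assume ALT/AST above 3×ULN in 30 to 50% and a spurious or non-concurrent TBIL elevation in 5 to 20%, independently, giving 36 × 0.30 × 0.05 = 0.5 to 36 × 0.50 × 0.20 = 3.6. Neither rate is in the documents. The second merges two mechanisms, independence is unsupported, and a true ALT rise followed by a true bilirubin rise would be counted as false.

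The documents support only the scale of a single participant, 2.8 percentage points at N = 36.

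**What to change.** In Section 2.8.3 of both SAPs, add combined rows that use DBIL only, with ALT/AST and DBIL from the same sample or visit:

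- **Normal baseline:** ALT or AST >3×ULN with DBIL >2×ULN, shown with and without the cholestasis exclusion as protocol 6.5.2.1 defines it. Table 6-7 and Section 6.5.2.1 differ on that clause; the protocol passages should be reconciled, and showing both versions keeps the table from having to choose.
- **Elevated baseline:** the protocol's baseline-relative thresholds, using the SAP's chemistry baseline.

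Keep the three existing TBIL-or-DBIL rows with the 30-day window as a broad screen, so that staggered rises are still captured. Label them as subject to TBIL assay interference and as not equivalent to the protocol criterion.

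The cost is a few extra descriptive rows and the programming of the baseline branch. ALT, AST, ALP and DBIL are already on the same chemistry panel (protocol Table 8-3), so no new data are needed and clinical management does not change.

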## **2.8.4 Other safety data**

### **2.8.4.1 ECG**

A standard 12 lead ECG will be performed:

- at screening or baseline (Triplicate ECG to be collected to assess QTcF intervals)
- at Week 13, Week 26 and Week 52 (in the extension part ECG is only for the responders)
- at the end of treatment

### **Data handling**

In case the study requires ECG replicates at any assessment, the average of the ECG parameters at that assessment should be used in the analyses.

### **Data analysis**

The following summaries will be produced for ECG results:

- Descriptive statistics including mean, SD, median, 25th and 75th percentiles, minimum, and maximum will be summarized for ECG values at each visit.
- The number and percentage of subjects with notable ECG values below at each visit will be presented.
  - QT, QTcF
    - New value of > 450 and  $\leq$  480 ms
    - New value of > 480 and  $\leq$  500 ms
    - New value of > 500 ms
    - Increase from Baseline of > 30 ms to  $\leq$  60ms
    - Increase from Baseline of > 60 ms
  - HR

- Increase from baseline >25% and to a value > 100 bpm
- Decrease from baseline >25% and to a value < 50 bpm
- PR
  - Increase from baseline >25% and to a value > 200 ms
  - New value of > 200 ms
- QRS
  - Increase from baseline >25% and to a value > 120 ms
  - New values of QRS > 120 ms

A listing of all ECG assessments will be produced and notable values will be flagged. In the listing, the assessments collected during the post-treatment period will be flagged.

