Additional, unscheduled, safety ECGs may be repeated at the discretion of the investigator at any time during the study as clinically indicated. For any ECGs with participant safety concerns, two additional ECGs must be performed to confirm the safety finding. Unscheduled ECGs with clinically significant findings should be collected in triplicate. The individual ECGs should be recorded approximately 2 minutes apart. Local cardiologist ECG assessment may also be performed at any time during the study at the discretion of the investigator. A monitoring or review process should be in place for clinically significant ECG findings throughout the study and especially at baseline before administration of study treatment.

Clinically significant abnormalities must be recorded on the CRF as either medical history/current medical conditions or AEs as appropriate. Clinically significant findings must be discussed with Novartis prior to enrolling the participant in the study. New or worsened clinically significant findings occurring after informed consent must be recorded as AEs.

In the event that a QTcF value of > 500 ms is observed or if an unscheduled ECG is performed for safety reasons, it is recommended to collect a ECG time-matched PK sample as unscheduled PK sample and record the time and date of the last investigational drug intake to determine the drug exposure. Dose adjustments in case of QT prolongation should be performed per [Section 6.5.1.1](#).

Paper ECGs should be appropriately labeled and kept in the source documents at the study site. If an unscheduled ECG is performed at an external medical facility, a copy of the ECG should be obtained and kept in the source documents at the study site.

8.4.2.1 **Cardiac imaging - echocardiogram**

An echocardiogram scan is required to be completed at screening. Clinically significant abnormalities present when the participant signed the informed consent should be reported as Medical History on the appropriate eCRF. New or worsened clinically significant findings occurring after informed consent must be recorded as an AEs on the eCRF.

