Summary tables for AEs will include only AEs that started or worsened during the on-treatment period, the **treatment-emergent** AEs.

The incidence of treatment-emergent AEs (new or worsening from baseline) will be summarized by system organ class and or preferred term, severity (based on CTCAE grades), type of AE, relation to study treatment.

SAEs, non-serious AEs and AESI during the on-treatment period will be tabulated.

All deaths (on-treatment and post-treatment) will be summarized.

All AEs, deaths, and SAEs (including those from the pre- and post-treatment periods) will be listed and those collected during the pre-treatment and post-treatment period will be flagged.

Vital signs

All vital signs data will be listed by participant, and visit/time and if ranges are available, abnormalities will be flagged. Summary statistics will be provided by treatment and visit/time.

12-lead ECG

PR, QRS, QT, QTcF and RR intervals will be obtained from 12-lead ECGs for each participant during the study.

Shift tables of ECG findings ('Normal' or 'Abnormal') from baseline to worst on-treatment result will be generated. Descriptive statistics at baseline, one or several post-baseline time points and change from baseline to this/these post-baseline time points will be presented.

ECG evaluations for all participants with at least 1 abnormality will be listed. All ECG data will be listed by participant and visit/time, abnormalities will be flagged.

Clinical laboratory evaluations

All laboratory data will be listed by participant and visit/time and if normal ranges are available, abnormalities will be flagged. Summary statistics will be provided by treatment and visit/time. Shift tables using CTCAE grades or the low/normal/high/ (low and high) classification will be used to compare baseline to the worst on-treatment value.

Grading of laboratory values will be assigned programmatically as per NCI Common Terminology Criteria for Adverse Events (CTCAE), version 4.03. The calculation of CTCAE grades will be based on the observed laboratory values only, clinical assessments will not be taken into account.

CTCAE Grade 0 will be assigned for all non-missing values not graded as 1 or higher. Grade 5 will not be used.

For laboratory tests where grades are not defined by CTCAE, results will be categorized as low/normal/high based on laboratory normal ranges.

The following summaries will be generated separately for hematology, and biochemistry tests:

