## Document History – Changes compared to previous final version of SAP

Date	Time point	Changes	Section and title impacted (Current)
15-Sep-2020	Prior to FPFV	N/A - First version	NA
1-Jul-2022	Prior to DBL	Update the definition of on-treatment period and post-treatment period according to protocol changes; Update the windows for multiple assessments	Section 2.1.1
		Remove the race subgroup analysis in efficacy, safety and PK; Update the China Mainland/Japan specific subgroup analysis	Section 2.2.1
		Update the definition of duration of exposure with consideration of using hours as unit time for rATG; Add the definition and the corresponding statistical analysis of actual duration of exposure	Section 2.4.1
		Add the definition and the corresponding statistical analysis of actual dose intensity; Remove the planned dose intensity and relative dose intensity	Section 2.4.1
		Remove the summary analysis and the corresponding table for concomitant medications that have the potential to impact efficacy results	Section 2.4.2
		Add the supplementary analysis section to specifically describe the CR response that is derived programmatically using laboratory results	Section 2.5.1; Section 2.5.4
		Update the definition of the relapse; Add the definition and corresponding statistical analysis for below-listed item: Time to response; Maximum duration of Platelet and RBC transfusion free;	Section 2.7

Date	Time point	Changes	Section and title impacted (Current)
		Proportion of subjects with transfusion decrease; Changes in platelet count, hemoglobin and neutrophil count	
		Specify that the CTC grade $\geq 3$ adverse events will be summarized for AEs by SOC and PT	Section 2.8.1
		Add the sub-items for ALT and AST	Section 2.8.3
		Remove the percentage summary table and the shifted table for ECG Findings	Section 2.8.4.1
		Update PD and PK/PD analyses	Section 2.10
		Update the definition of the cytogenetic abnormalities and clonal evolution observed during the study; Remove the time to clonal evolution	Section 2.12
		Add the imputation rule of end dates, when missing component is the hour for rATG	Section 5.1.2

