# 4 Change to protocol specified analyses

Below-listed endpoints were added to further support efficacy analysis beyond protocol.

- Time to response
- Maximum duration of Platelet and RBC transfusion free

- Proportion of subjects with transfusion decrease
- Changes in platelet count, hemoglobin and neutrophil count

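### Both SAPs count notable ECG values by visit only and give no rule for unscheduled ECGs, so no planned ECG table shows how many participants were ever affected

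*SAP*

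**What the plan says.** Protocol 12.5.2 (12-lead ECG) plans a worst-case display: "Shift tables of ECG findings ('Normal' or 'Abnormal') from baseline to worst on-treatment result will be generated". It also plans descriptive statistics at baseline and post-baseline time points, and listings.

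The primary-analysis SAP, in its document history entry of 1-Jul-2022 for Section 2.8.4.1, records: "Remove the percentage summary table and the shifted table for ECG Findings". Two ECG summaries remain in Section 2.8.4.1, and both are by visit: descriptive statistics, and the notable-value table, for which "The number and percentage of subjects with notable ECG values below at each visit will be presented". The QT/QTcF categories include "New value of > 500 ms" and an increase from baseline above 60 ms. The final-analysis SAP repeats this section. Both SAPs also list every ECG assessment with notable values flagged.

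Section 4 of each SAP, on changes to protocol-specified analyses, is confined to additions: "Below-listed endpoints were added to further support efficacy analysis beyond protocol". The ECG removal is not there. The final-analysis SAP's document history calls that document a first version, so it does not mention the removal anywhere.

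Scheduled post-baseline ECGs fall "at Week 13, Week 26 and Week 52 (in the extension part ECG is only for the responders"), and at end of treatment. Protocol 8.4.2 also foresees others: "Additional, unscheduled, safety ECGs may be repeated at the discretion of the investigator at any time during the study as clinically indicated".

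**The concern.** The frequency of ECG abnormalities is part of a secondary endpoint (Protocol Table 2-1; SAP Table 1-1). The natural measure is the number of participants who ever had a notable value. A by-visit table does not give it, because the same person may be counted at several visits or different people at each.

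Unscheduled ECGs make this worse. They are done because something looks wrong, so they are a likely place for an extreme QTcF to be found. Protocol 8.4.2 links the two when it recommends a time-matched PK sample: "In the event that a QTcF value of > 500 ms is observed or if an unscheduled ECG is performed for safety reasons". The SAPs do not say which visit column, if any, such an ECG enters. The programmer would have to decide once data exist.

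QTcF above 500 ms also matters for conduct. Under Protocol 6.5.1.1 a confirmed value leads to interruption of eltrombopag, and recurrence after dose reduction leads to discontinuation. A reader of the study report will want to know how many participants crossed that threshold.

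**Working it through.** The plan states no figure for this point, so there is none to reproduce. The check compares the texts and then applies a simple bound.

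**1. Is there any ECG summary not tied to a visit?** Protocol 12.5.2 had one, the shift to worst on-treatment result. Section 2.8.4.1 of either SAP has none.

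**2. How does ECG compare with other safety data in the same SAPs?**
- Laboratory data (2.8.3): worst post-baseline grade, and shift from baseline to worst on-treatment value.
- Liver parameters (2.8.3): worst post-baseline values.
- Notable vital signs (2.8.4.2): number and percentage of participants, not restricted to each visit.
- ECG (2.8.4.1): by visit only.

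**3. Is there a rule for unscheduled ECGs?** The windows in SAP 2.1.1, with their preference for scheduled over unscheduled assessments, are written for hematological response. Nothing equivalent covers ECG. The SAPs neither include unscheduled ECGs in the by-visit table nor exclude them.

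**4. How sparse are the scheduled ECGs?** Protocol Table 8-1 has an ECG at screening or Day 1, then at Week 13 (Day 92), Week 26, Week 52 and end of treatment, which is at most four post-baseline time points. For a participant who stays on eltrombopag, nominal Days 2 to 91 (91 − 2 + 1 = 90 days) carry no scheduled ECG.

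**5. What can by-visit counts say about the number ever affected?** Let x_v be the count at time point v and n the number of participants. The number ever affected at scheduled ECGs lies between max(x_v) and min(n, Σx_v).

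Illustration, with assumed inputs: n = 36 (the planned sample size), everyone has an ECG at all four time points, and x_v = 1 at each.
- Lower bound: max = 1, so 1/36 = 2.8% (exact 95% CI 0.1 to 14.5).
- Upper bound: 1 + 1 + 1 + 1 = 4, so 4/36 = 11.1% (exact 95% CI 3.1 to 26.1).
- If one further participant had the value only on an unscheduled ECG, the upper end becomes 5/36 = 13.9% (exact 95% CI 4.7 to 29.5).

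The four by-visit cells read 1/36 (2.8%) at either end of the 1-to-4 range. They would read the same with the fifth participant if that ECG were left out of the visit columns.

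**The case against.** The strongest reply is that no information is lost. Every ECG is listed with notable values flagged, and with about 36 participants the number ever affected can be counted by hand. New or worsened clinically significant ECG findings must be recorded as adverse events (Protocol 8.4.2). On-treatment adverse events are tabulated in SAP 2.8.1, including those leading to dose interruption or discontinuation, and interruptions with their reasons are summarised in 2.4.1. The SAP's numeric categories also go beyond the dropped protocol table. That table classed findings only as normal or abnormal and would never have counted QTcF above 500 ms. Its removal was recorded before database lock.

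Much of this stands, and it rules out several stronger readings:
- A reader might infer that a QTcF above 500 ms on an unscheduled ECG would appear in no table, or be counted as zero. The SAPs are silent on unscheduled ECGs and do not exclude them, and the adverse event tables are a second route.
- A reader might infer that any event before Week 13 could come only from an unscheduled ECG. A participant who stops eltrombopag early has a scheduled end-of-treatment ECG.
- A reader might infer that the protocol interrupts treatment on a rise above 60 ms. Protocol 6.5.1.1 starts a confirmation work-up for such a rise, and interruption at that stage is conditional.
- A reader might infer that restoring the shift table would cure the problem. It would not give the threshold counts.

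The reply does not close the gap. A listing gives no frequency or denominator, and the endpoint is a frequency. The adverse event route depends on a judgement of clinical significance and counts preferred terms, not the SAP's millisecond criteria. Silence on unscheduled ECGs leaves the choice until after the data are seen.

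**Conclusion.** The point holds as a gap in safety reporting. In both SAPs the ECG summaries are by visit only, unscheduled ECGs have no assignment rule, and the protocol's worst on-treatment table is gone without an entry in Section 4. A QTcF above 500 ms or a rise above 60 ms seen only on an unscheduled ECG is assured of a place in the listing, and in the adverse event tables only if judged clinically significant.

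The size can only be illustrated: identical by-visit cells of 1/36 fit 2.8% to 11.1% of participants ever affected. This assumes 36 participants with an ECG at all four time points. Actual denominators would fall after Week 26, because only responders continue. The documents give no expected rate of QTcF events, so the number that might be missed cannot be estimated. No efficacy estimate is affected.

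**What to change.** In Section 2.8.4.1 of both SAPs:
- Add, for each notable ECG criterion, the number and percentage of participants meeting it at any time in the on-treatment period as defined in 2.1.1.
- Use each participant's worst value over scheduled and unscheduled ECGs, and say whether the existing replicate-averaging rule applies to unscheduled triplicates.
- Take as denominator the participants with a baseline and at least one post-baseline ECG.

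Either restore the baseline-to-worst shift table or declare its removal in Section 4 of both SAPs. The cost is one extra row or column in an existing table, and a sentence in Section 4 if the removal stands. No new data are needed.
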